### **5.2.5. Baseline Physical Examination**

Overall assessment of baseline physical exam (categorized as normal, abnormal, or not performed) will be summarized by number and percentage, together with post-baseline data.

### **5.2.6. Baseline Vital Signs**

Baseline vital signs including systolic and diastolic blood pressures (mmHg), heart rate (pulse [beats/min]), respiratory rate (breaths/min), and body temperature (°C) will be summarized using descriptive statistics, together with post-baseline data.

## **5.3. Exposure and Treatment Compliance**

Study drug exposure will be summarized for the cipaglucosidase alfa/miglustat combination treatment rather than separately for cipaglucosidase alfa and miglustat. All analyses will be based on the exposure during Study ATB200-07 only.

Analyses will be presented by treatment groups Cipaglucosidase alfa/miglustat–Cipaglucosidase alfa/miglustat, Alglucosidase alfa/placebo–Cipaglucosidase alfa/miglustat, and overall, as defined in Section 4.2. The duration of treatment (ie, extent of exposure), in months, will be calculated as (date of last dose in ATB200-07 – date of first dose in ATB200-07 + 1) / 30.4, and summarized using descriptive statistics (n, mean, SD, median, minimum, and maximum).

In addition, the duration of treatment will be categorized into the exposure intervals below and summarized using number and percentages of subjects:

≤ 3 months, > 3 to ≤ 6 months, > 6 to ≤ 9 months, > 9 to ≤ 12 months, > 12 to ≤ 18 months, > 18 to ≤ 24 months, > 24 to ≤ 36 months, > 36 to ≤ 48 months, > 48 months to ≤ 60 months, and > 60 months.

Additionally, a summary of the duration of treatment (exposure) will be provided by prior ERT status.

### **5.3.1. Study Compliance**

Compliance will be provided separately for cipaglucosidase alfa and miglustat. For each subject taking cipaglucosidase alfa, compliance will be calculated based on the number of infusions as well as the actual infusion dose administered.

Compliance based on infusion dose is calculated as:

100\*(total infusion dose administered [mg] / total infusion dose planned or intended [mg]).

Compliance based on number of infusions is calculated as:

100\*(number of infusions administered / number of infusions planned or intended),

where the number of infusions planned is obtained as: (subject's last date in ATB200-07 as of the data cut-off date – date of first infusion + 14) / 14.

Compliance for each subject taking miglustat will be calculated as:

100\*(total dose administered [mg] / planned dose [mg]).

Dose compliance rate will be classified as under-compliance: < 80%, within compliance: (80%, 120%), and over-compliance: > 120%.

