### **9.3. Withdrawal Criteria**

Subjects may withdraw or be withdrawn from the study for any reason, including, but not limited to, the following:

- at their own request
- if, in the investigator's opinion, continuation in the study would be detrimental to the subject's well-being

Note: Subjects with serious adverse events (SAEs) of anaphylaxis to cipaglucosidase alfa must be withdrawn from the study.

- if, in the investigator's opinion, there is a lack of efficacy for the subject
- persistent noncompliance with study requirements, such as failure to comply with the study visit schedule, in the judgment of the investigator and/or medical monitor
- persistent noncompliance with study drug or failure to return to the study site for infusion visits, in the judgment of the investigator and/or medical monitor
- inability to contact subject (ie, subject is lost to follow-up)
- pregnancy (female subjects)
- planning to conceive a child (male or female subjects)
- sponsor decision to terminate the study

In all cases, the reason for withdrawal and the date of withdrawal must be recorded in the electronic case report form (eCRF) and in the subject's medical records.

Subjects who withdraw will be requested to complete the Early Termination Visit. The investigator will make every effort to contact withdrawing subjects and schedule the early termination assessments. Upon study completion or subject discontinuation, subjects who are confirmed positive for anti-rhGAA antibodies will complete follow-up immunological testing for up to 12 months after the last dose of study drug (ie, at 6 months and 12 months) or until they begin treatment with an investigational therapy or an ERT that is approved by the local health authority and is commercially available (see [12.2.6](#)).

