**Table 4: Schedule of Assessments for Subjects Who Participated in Study ATB200-03**

Study Visit	Baseline a	Day 1 b	Treatment				Follow-up ≥ 30 Days After Last Dose
			Infusion Visits (Every 2 Weeks Through EOS/ET)	Weeks 2, 4, 6	Weeks 12, 26, and then Every 26 Weeks c	EOS/ ET	
Visit Window (Days)	—	± 3	± 3	± 3	± 3	± 3	± 3
Administrative							
Informed consent (12.2.1)	X						
Eligibility criteria (9.2.1)	X	X					
Demographics (12.3.1)	X						
Schedule next visit	X	X	X	X	X	X	
Clinical Assessment							
Medical history (12.3.2)	X						
Prior/concomitant medications and nondrug therapies (12.3.3)	X	X	X	X	X	X	X
Complete PE (12.3.4)	X						X
Brief PE (12.3.4)				X	X		
Vital signs (12.3.6)	X	X	X	X	X	X	
Weight d (12.3.5)	X				X		X
Height (12.3.5)	X						
AEs/SAEs, including IARs (13)	X	X	X	X	X	X	X

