#### **12.2.5. End of Study/Early Termination**

Subjects who complete the study or discontinue study drug for any reason will be asked to return for the End of Study/Early Termination Visit. The End of Study visit is performed as the final full assessment visit for a subject who has completed the study as defined in Section 8.5. The Early Termination visit is performed as the final full assessment visit for a subject who ends treatment with the study drugs prior to completing study treatment.

If infusions were missed close to the scheduled assessments on the last week of the study, it should be communicated with Amicus to determine on a case-by-case basis whether catch-up infusions are needed and how many catch-up infusions are needed prior to the study assessments.

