#### **12.2.6. Follow-up Period**

A 30-day safety follow-up visit for monitoring of any AEs that were ongoing at end of study should be conducted.

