#### **13.3.3. Missed Dose**

If a subject is unable to schedule a treatment (infusion) up to 7 days after the scheduled date, this is considered as a missed dose. The subject will receive his or her next dose per his or her schedule, ie, approximately 4 weeks following the previous dose, since the subject missed a dose at 2 weeks following the last dose. This is recorded as a protocol deviation. Any AE that occurs as a result of missed dose should be recorded as such. The Amicus medical monitor should be notified as soon as feasible after the investigator or study personnel first become aware of the missed dose. Follow-up information on the outcome must be forwarded as applicable. If an SAE occurs in conjunction with the missed dose, the same SAE reporting requirements described in Section 13.3 apply.

Study subjects who missed infusions close to their scheduled assessments at Week 12, Week 26, or at any of the study visits scheduled every 26 weeks after Week 26 should postpone the assessments and receive a sufficient number of catch-up infusions prior to undergoing the study assessments. Each instance of missed infusion should be discussed with, and course of action approved by, the medical monitor. A reason for the missed visit should be entered into the EDC. The relevant IRBs, IECs, and REBs should be notified of any deviations from the protocol.

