### **3. STUDY DESIGN**

#### **3.1. Summary of Study Design**

This is a multicenter, international, OLE study of ATB200/AT2221 (heretofore referred to as cipaglucosidase alfa/miglustat) in adult subjects with late-onset Pompe disease (LOPD) who completed the randomized double-blind Study ATB200-03. Study ATB200-07 consists of a treatment period that lasts until 31 December 2024 or until study termination by the sponsor, and it includes a 30-day safety follow-up period for the end of study (EOS) or early termination (ET) assessments.

All subjects in Study ATB200-07 are to be treated with cipaglucosidase alfa/miglustat every 2 weeks. Subjects who previously received alglucosidase alfa/placebo in Study ATB200-03 were switched to cipaglucosidase alfa/miglustat in Study ATB200-07, and subjects who received cipaglucosidase alfa/miglustat in Study ATB200-03 continued on cipaglucosidase alfa/miglustat in Study ATB200-07. The first infusion visit in this study was to be scheduled approximately 2 weeks after the last visit in Study ATB200-03 in an effort to ensure continued administration of study drug on the same schedule with no gap between studies. The end of study assessment in Study ATB200-03 will be considered the baseline assessment in Study ATB200-07, as described in Section 4.4.2.

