### 5.1. Subject Disposition

Disposition will focus on Study ATB200-07 only, and it will be presented by the treatment groups described in Section 4.2 and overall. The presentation will include the number of subjects who enrolled in the OLE study (OLE-ES), the number and percentage of subjects in the FAS, and the OLE safety population, number and percent of subjects who completed the study (based on the ‘Yes’ check box on the eCRF), and who discontinued the study early. The categories classifying the subjects’ study completion status are derived from the end of study electronic case report form (eCRF) page. The number and percent of subjects by reason of discontinuation will also be presented. As much as possible, any discontinuation with reason due to ‘other’ will be queried and re-categorized appropriately, by medical review.

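### Does the undefined end date in the planned-infusion count make the compliance summary unreliable?

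*SAP*

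**What the plan says.** SAP 5.3.1 defines infusion-count compliance as 100 times infusions administered over infusions planned. Planned infusions run from the first infusion to the subject's "last date in ATB200-07 as of the data cut-off date"; 14 is added to the difference in days and the sum is divided by 14. The section does not say whether the last date is a dose, a visit, a withdrawal or a contact, and it gives no rounding rule.

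Neighbouring text bears on the choice of date:

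- SAP 4.4.1 and SAP 5.3, the parent section, both end exposure at the last dose.
- SAP 3.1 says of the study that "it includes a 30-day safety follow-up period for the end of study (EOS) or early termination (ET) assessments".
- Protocol Table 4 labels the dosing column "Infusion Visits (Every 2 Weeks Through EOS/ET" and places the follow-up column at 30 days or more after the last dose.
- Protocol 12.2.6 describes that contact: "A 30-day safety follow-up visit for monitoring of any AEs that were ongoing at end of study should be conducted".
- Protocol 12.2.5 says: "The Early Termination visit is performed as the final full assessment visit for a subject who ends treatment with the study drugs".
- Protocol 9.3 requires a withdrawal date on the eCRF, and SAP 5.1 says the completion categories "are derived from the end of study electronic case report form (eCRF) page".
- Protocol 10 bases treatment compliance on the drug administration records.

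The class of under-compliance below 80% in SAP 5.3.1 is worded for dose compliance, not for the infusion count.

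**The concern.** The formula turns elapsed time into expected infusions, so the end date fixes the denominator. SAP 3.1 places a 30-day safety follow-up inside the study. A reader could therefore take the last date of a subject who has stopped to be the follow-up date. That adds 30/14 = 2.14 expected infusions for a period in which Table 4 plans none.

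Separately, an end date between two scheduled infusions adds a fraction, up to 13/14, of an infusion not yet due. This can happen to anyone still on treatment at the 31 December 2024 cutoff.

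Either way, a fully adherent subject can be reported below 100%, and two programmers could report different values for the same subject. Short-exposure subjects would be affected most.

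**Working it through.** **Inputs.** The dosing interval is 14 days (Protocol 10). The planned count is (last date − first infusion + 14)/14 (SAP 5.3.1). Follow-up is at 30 days (SAP 3.1, Protocol 12.2.6). Visit windows are ±3 days (Protocol Table 4). The documents state no compliance figure to reproduce and give no subject-level dates, so the values of n and f below are assumptions.

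**Formula.** Take n infusions exactly 14 days apart and an end date f days after the last one:

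planned = ((n − 1) × 14 + f + 14)/14 = n + f/14

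compliance = 100 × n/(n + f/14)

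**Results for a fully adherent subject**

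| End date | f | n = 8 | n = 26 | n = 104 |
|---|---|---|---|---|
| Last dose | 0 | 100% | 100% | 100% |
| Cutoff just before next infusion | 13 | 8/8.93 = 89.6% | 26/26.93 = 96.6% | 104/104.93 = 99.1% |
| EOS/ET visit, assumed 14 days after last infusion | 14 | 8/9 = 88.9% | 26/27 = 96.3% | 104/105 = 99.0% |
| Safety follow-up | 30 | 8/10.14 = 78.9% | 26/28.14 = 92.4% | 104/106.14 = 98.0% |

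A subject dosed through Week 234 has 234/2 + 1 = 118 infusions. The result is then 118/118.93 = 99.2% at f = 13 and 118/120.14 = 98.2% at f = 30.

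**Which reading fits.** The added 14 makes the count exact when the end date is the last infusion, and the parent section ends exposure there. The protocol's end-of-study and early-termination text supports the EOS/ET date instead. Both dates are tied to treatment. The follow-up reading has the least support: SAP 3.1 attaches the 30 days to the EOS/ET assessments, and Protocol 12.2.6 treats the follow-up as coming after end of study.

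**Would last dose be a safe default?** Not entirely. Suppose 26 infusions were scheduled, the last two were missed, and the last dose was on day 322 after the first. Planned is then (322 + 14)/14 = 24 and compliance is 24/24 = 100%. Against the schedule it is 24/26 = 92.3%. Each anchor has a cost.

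**Would whole-infusion counting be better?** Take planned = floor((end − first)/14) + 1.

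- The eighth infusion is due on day 98, is given one day early on day 97, and the cutoff is day 97. Floor gives 6 + 1 = 7, so compliance is 8/7 = 114.3%. The present formula gives (97 + 14)/14 = 7.93 and 8/7.93 = 100.9%.
- An EOS visit falls 17 days after the last of 8 infusions, on day 115. Floor gives 8 + 1 = 9 and 8/9 = 88.9%, so 100% is not restored. Excluding the untaken infusion would need the date of the decision to stop study drug. Protocol 9.3 shows only that a withdrawal date is recorded.

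**The case for a change.** The best argument for a change is that SAP 5.3.1 uses different words from SAP 4.4.1 and 5.3, which both name the last dose. The authors may therefore have meant something else, and no other section says what. The protocol cannot settle it, because SAP section 1 says the SAP supersedes the protocol's methods. The rounding point also survives whichever anchor is chosen, except last dose.

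Short exposure is provided for in the SAP 5.3 categories, and there the readings differ by up to 21.1 points (100% against 78.9% at 8 infusions). The literal reading can be pushed further: Protocol 9.3 allows antibody testing up to 12 months after the last dose. If that counted, f = 365 would give 104/(104 + 26.07) = 80.0% even at 104 infusions.

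It stands that the term is undefined and that the arithmetic is right. It does not stand that the formula is biased in itself: the shortfall comes from choosing an end date after dosing has stopped, or from an ordinary fractional count. The 12-month case tells against the literal reading, since no analyst would count infusions as planned a year after treatment ended. Dividing days by 14 also suits a schedule that a missed dose does not shift; Protocol 13.3.3 says "The subject will receive his or her next dose per his or her schedule".

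**Conclusion.** No change to the plan follows. SAP 5.3.1 leaves out a detail that an analyst would fill sensibly, by choosing a date tied to treatment and recording it in the programming specification.

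For long-treated subjects (104 infusions or more) the shortfall is at most about 1 point with the EOS/ET or cutoff date and about 2 points with the follow-up date. Only an early stopper on the least-supported of the main readings falls below 80%. Even then the under-compliance class would be reached only if planned milligrams were built from the same count, which the SAP does not say. Infusion-count compliance is descriptive: it defines no analysis set, and no safety or efficacy conclusion depends on it.

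A whole-infusion rule would trade one small distortion for another, and a decision-date rule needs a date the documents do not show is collected.

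These sizes assume perfect 14-day dosing and the lags shown. The documents do not say how many subjects stopped early. If many stopped within the first few months, the summary would be more sensitive to the chosen date, but its role in the report would be the same.

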## 6. ANALYSIS OF EFFICACY AND PHARMACODYNAMICS

### 6.1. Analysis of Efficacy Endpoints

No formal hypotheses are planned to be tested. Unless otherwise specified, only descriptive statistics will be presented. Any inferential statistics will be presented for summary purposes.

Efficacy endpoints are described in Section 2.3.2. Continuous variables will be summarized using descriptive statistics for the actual values and for the change from baseline. A 95% confidence interval (CI) for the mean change from baseline will be included for summary purposes. That is:

- For the Actual values (ie, baseline or visit values): the summary will present n, mean, SD, median, Q1, Q3, minimum, and maximum.
- For change from baseline values: the summary will present n, mean, SD, 95% CI, median, Q1, Q3, minimum, and maximum.

Categorical variables will be summarized using counts and percentages. Efficacy analysis will be performed on the FAS population (as defined in Section 4.1.3), and it will be presented by visit and by treatment group (and overall, if appropriate). Line plots of the mean  $\pm$  standard error (SE) of the change from baseline over time will be provided for the 6MWD and % predicted FVC (see Section 2.3.2.1 for clarification).

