## **8.2. Duration of Study**

The study will consist of a treatment period that lasts until one of the following conditions apply:

- the product is approved and commercialized for use in the investigational study population, or
- cipaglucosidase alfa/miglustat is rejected by the regulatory authority in the subject's local country as an approved treatment for Pompe disease, or
- the sponsor decides to continue to provide cipaglucosidase alfa/miglustat via a post-trial access mechanism, or
- the subject is withdrawn or withdraws consent, or
- the sponsor decides to end the study.

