#### **15.3.3.3. Missing Data Handling**

For all efficacy endpoints based on patient-reported outcome/clinical outcome assessment instruments, the scoring algorithms (including the standard or published data imputation or pro-rating methods contained in the scoring algorithms) will be implemented.

No data imputation are planned for missing efficacy data. If any imputations are decided upon later, the details will be provided in the statistical analysis plan.

In general, missing safety data will not be imputed. However, attributes such as missing dates for AEs and concomitant medications will be imputed using similar methods as described for ATB200-03 in order to ensure consistency. Details will be provided in the statistical analysis plan.

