#### **4.6.2. Imputation for Missing Post-baseline Values**

Missing post-baseline values (whether efficacy or safety) will not be imputed.

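### Long-term 6MWD and sitting % predicted FVC are shown only for subjects observed at each visit; if exit is related to decline, the later curve understates decline, and no planned display links exit to trajectory

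*SAP*

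**What the plan says.** SAP 6.1 sets the efficacy analysis on the FAS and says that "it will be presented by visit and by treatment group (and overall, if appropriate". "Unless otherwise specified, only descriptive statistics will be presented", and "For change from baseline values: the summary will present n, mean, SD, 95% CI, median, Q1, Q3, minimum, and maximum". The plots are line plots of mean and "standard error (SE) of the change from baseline over time will be provided for the 6MWD and % predicted FVC". SAP 6.3 repeats the by-visit summaries and these two plots by prior ERT status.

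On missing data, SAP 4.6.2 says "Missing post-baseline values (whether efficacy or safety) will not be imputed", and Protocol 15.3.3.3 agrees: "No data imputation are planned for missing efficacy data". SAP 4.1.3 admits a subject to the FAS with a baseline and one post-baseline value on any one of six endpoints, so no fixed cohort is implied at later visits.

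On exit, Protocol 9.3 allows withdrawal if the investigator judges that "there is a lack of efficacy for the subject". Protocol 8.2 ends treatment for other reasons as well; the first listed is "the product is approved and commercialized for use in the investigational study population, or" and the list continues with regulatory rejection and post-trial access. Protocol 8.5 counts transfer to commercial or post-trial drug as completion. SAP section 1 applies one calendar cutoff, 31 December 2024. The last efficacy window, Week 234, takes everything after Day 1548 (SAP Table 3).

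**The concern.** A line joining by-visit means looks like the course of one group of people. Here each point comes from a different and smaller set. A subject who leaves contributes up to the last assessment and to no later point. If leavers were declining faster than those who stayed, the later means move towards the stayers.

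This matters most late in follow-up. Protocol 6.6 describes alternative treatments as helping most subjects for 2 to 3 years before a slow decline, and Protocol 6.1 presents this product as addressing duration of effect. Plateau or decline after Year 3 is therefore what a reader will look for, and these are the only two efficacy endpoints plotted. The later addendum will not settle it: under Appendix 1, section 15.3.4, it uses only data after database lock, with a reset baseline and no integration with earlier data.

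**Working it through.** The plan states no power, exit rate, slope or SD, so there is no figure of its own to reproduce. The check has three steps.

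**1. Is there any analysis beyond observed cases?** SAP 4.1.3, 4.5.3, 4.6.2, 6.1 and 6.3 and Protocol 15.3 contain no mixed model, no constant-cohort display, no display by time of exit and no missing-data sensitivity analysis. SAP 6.1 puts n in the tables but does not say that it will appear on the plots. SAP 5.1 tabulates reasons for discontinuation, but not against the leavers' 6MWD or FVC.

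**2. How far could the 6MWD curve move?** From the documents: about 110 subjects, visits every 26 weeks, last window Week 234 (234/52 = 4.5 years). Assumed:
- Change for subject i at time t is b_i × t + e, with b_i normal (mean -8 m/year, SD 12 or 6) and e normal (SD 20 m). The true mean at 4.5 years is -8 × 4.5 = -36 m.
- Decline-related exit before each visit: logit(p) = logit(p0) + g × (metres lost at the previous visit), with g = 0, 0.02 or 0.03. p0, the risk at zero loss, is either 2.7% or set lower so that average exit is 2.5% per 6 months.
- Exit unrelated to decline: 15% per 6 months after Year 2.5.

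Results from 3,000 simulated data sets per row:

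| Slope SD | g | Average decline-related exit per 6 months | n at 4.5 y | Observed mean, 2 y | 3 y | 4.5 y | Error at 4.5 y |
|---|---|---|---|---|---|---|---|
| truth | | | | -16 | -24 | -36 | |
| 12 | 0 | 2.7% (unrelated) | 46 | -16.0 | -24.0 | -35.9 | none |
| 12 | 0.02 | 2.5% | 46 | -15.6 | -22.5 | -29.3 | 7 m |
| 12 | 0.02 | 4.4% | 39 | -15.3 | -21.4 | -24.9 | 11 m |
| 12 | 0.03 | 2.5% | 46 | -15.5 | -22.0 | -26.0 | 10 m |
| 12 | 0.03 | 5.8% | 34 | -14.8 | -19.0 | -15.8 | 20 m |
| 6 | 0.02 | 2.5% | 46 | -15.9 | -23.6 | -34.3 | 2 m |
| 6 | 0.02 | 4.1% | 40 | -15.8 | -23.4 | -33.3 | 3 m |
| 6 | 0.03 | 2.5% | 46 | -15.9 | -23.5 | -33.4 | 3 m |
| 6 | 0.03 | 5.3% | 36 | -15.7 | -22.8 | -30.7 | 5 m |

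At 2 years the error is about 1 m or less in every row; it builds up later. Only the 5.8% row turns upward (-19.3 m at 3.5 years, -15.8 m at 4.5), and there about 40 of 110 subjects leave by the decline-related route. The 15% unrelated exit shrinks n but causes no error by itself.

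For FVC, a separate simulation assumed -1 point/year, residual SD 4, and exit of 4% per 26 weeks at the average slope, with log-odds rising 0.5 per SD of worse slope. At Week 234 the observed mean was -2.9 points (slope SD 2) or -2.1 points (slope SD 3), against -4.5 for all subjects. With unrelated exit it matched to within 0.1 point.

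**3. Would a likelihood model help?** In the scenarios of step 2, exit depends on an observed value, so missing-at-random holds. A random-slope maximum-likelihood fit returned -35.3 to -35.7 m in every row, including the row with unrelated exit, so the small gap from -36 m is simulation noise. If exit depends on the unobserved slope, the repair is partial. With -10 m/year, slope SD 25, residual SD 25, 4% exit and log-odds 1 per SD, the observed mean was -5.9 m, the model gave -32.4 m, and all subjects averaged -44.2 m.

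**The case against.** Efficacy is not a primary objective (Protocol 8.6), nothing is tested, and no decision rests on these plots. The tables give n, median, quartiles and a 95% CI as well as means. Leavers count at every visit they attended. They are asked to attend an Early Termination visit with 6MWT and FVC, and the day-based windows accept scheduled and unscheduled assessments, so a final decline can enter the summary once. Reasons for discontinuation are tabulated by treatment group and by prior ERT status. Commercial availability and the cutoff depend on country and calendar. The model recovers the truth in step 2 partly because the simulated decline is linear and so is the model.

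Most of this stands, and it keeps the point at the level of a worthwhile improvement. It does not remove it. All the tabulated statistics are still observed-case, the Early Termination value informs one window only, and neither n nor the reason for leaving shows whether leavers were declining.

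A reader might infer that the plotted curve will turn upward, or that a plateau could never be told from loss of decliners. The documents support neither. They give no rate for withdrawal for lack of efficacy, and in the simulation an upturn appeared only with heavy decline-related exit. Nor does every departure select on outcome: administrative exit unrelated to decline leaves the mean unbiased.

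**Conclusion.** The point holds conditionally. As written, the plan shows 6MWD and sitting % predicted FVC over time only for those observed, while the protocol provides an outcome-related way out. If exit is related to decline, the late curve understates it. For 6MWD at 4.5 years the observed mean lies between about -34 m and -16 m against a true -36 m, an error of about 2 to 20 m. This is for slope SD 6 to 12 m/year and average decline-related exit of 2.5% to 6% per 6 months. The usual appearance is flattening. If exit is unrelated to decline, there is no bias. All these sizes rest on assumed slopes, SDs and exit rates, because the documents give none. The consequence is for interpreting long-term efficacy, not for any test or for the primary safety objective.

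**What to change.** In SAP 6.1, for 6MWD and sitting % predicted FVC:

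1. Print n under every plotted visit.
2. Add a table of mean change by visit, split by last attended visit (before Week 104, before Week 208, still followed), with administrative exits (commercial or post-trial access, data cutoff) separated from other withdrawals. This shows directly, with few assumptions, whether leavers were declining.
3. Add a supportive descriptive analysis: a likelihood-based mixed model for change from baseline, with baseline value, treatment group, time and group-by-time. Plot its estimates with 95% CI beside the observed means. State that it relies on missing-at-random and corrects only partly if exit depends on unobserved decline.

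Items 1 and 2 are the most robust. Item 3 fits SAP 6.1, which already allows inferential statistics for summary purposes, and it imputes nothing, so SAP 4.6.2 can stand.

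The cost is SAP text, one table per endpoint, two models and two plots, all on data already collected. The downsides are a model assumption to state and some small groups in the exit table. Efficacy stays secondary and descriptive.
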